5.2 Phase Ib Dose Escalation

Dose escalation will involve only Ixazomib, increasing from 2.3 mg and then to 3 mg. Patients in each cohort will continue to the completion of the second cycle, and undergo evaluation of toxicity/tolerability prior to consideration of dose-escalation to the next cohort. The maximal dose of Ixazomib at 4mg was determined as in aforementioned myeloma studies.

Dose Cohort	Number of patients	TAK-659 (PO) Days 1-15	Ixazomib (PO) Days 1, 8, 15
1	3-6	100 mg, once daily	2.3 mg
2	3-6	100 mg, once daily	3 mg
3	3-6	100 mg, once daily	4 mg

Patients within each cohort will be followed for toxicity occurring within the first 2 cycles prior to initiating a dose/schedule escalation of the individual drugs in the next cohort, in context of the type of dose limiting toxicity (DLT) observed and to what study drug(s) the toxicity is related.

In cohort 1, If 1/3 patients develop grade ≥ 3 DLT toxicity, then 3 more patients will be entered at this dosing level; if $< 2/6$ patients develop DLT, then the next cohort will involve escalation of Ixazomib in dose.

If, on the other hand, toxicity attributable to the combination is seen in the first cohort at ≥ 2 patients, then we will consider modification of the protocol to reduce the initial dose of TAK-659 and/or Ixazomib. Again, our prior experience involving the addition of pharmacodynamically-active dosing as starting to a combination of Sorafenib and Vorinostat suggest we will not see this reduction as necessary. The dose modification plan will be based on the nature of the DLT:

Dose Cohort	Number of patients	TAK-659* (PO) Days 1-15	Ixazomib* (PO) Days 1, 8, 15
1	3-6	100 mg, once daily	2.3 mg
Dose modification plan			
		80 mg, once daily	2.3 mg Contact sponsor-investigator for consideration of schedule below 2.3mg.

*On clinic days for PK determination, TAK-659 will be taken first and then Ixazomib.

In cohort 2, if 1/3 patients develop grade ≥ 3 DLT toxicity, then 3 more patients will be entered at this dosing level; if < 2/6 patients develop DLT, then the next cohort will involve escalation of Ixazomib in dose.

Dose Cohort	Number of patients	TAK-659* (PO) Days 1-15	Ixazomib* (PO) Days 1, 8, 15
2	3-6	100 mg, once daily	3 mg
Dose modification plan based on the nature of DLT			
If DLT at least possibly related to TAK-659 OR not related to Ixazomib			
		80 mg, once daily	3 mg
If DLT at least possibly related to Ixazomib OR not related to TAK-659			
		100 mg, once daily	2.3 mg
If DLT at least possibly related to TAK-659 AND Ixazomib			
		80 mg, once daily	2.3 mg
*On clinic days for PK determination, TAK-659 will be taken first and then Ixazomib.			

In cohort 3, if $\geq 2/6$ patients develop DLT, a consultation will be made between the sponsor and investigators: either the previous dose level will be considered the MTD (if 6 or more patients have been studied at that dose level), the previous dose level will be expanded (if fewer than 6 patients have been studied at that dose level), or we will modify the the protocol to add a dose level intermediate between the current and the previous dose level.

Dose Cohort	Number of patients	TAK-659* (PO) Days 1-15	Ixazomib* (PO) Days 1, 8, 15
3	3-6	100 mg, once daily	4 mg
Dose modification plan based on the nature of DLT			
If DLT at least possibly related to TAK-659 OR not related to Ixazomib			
		80 mg, once daily	4 mg
If DLT at least possibly related to Ixazomib OR not related to TAK-659			
		100 mg, once daily	3 mg
If DLT at least possibly related to TAK-659 AND Ixazomib			
		80 mg, once daily	3 mg
*On clinic days for PK determination, TAK-659 will be taken first and then Ixazomib.			

As in usual protocol for MTD/RP2D determination, dose escalation will continue until these endpoints are determined based on safety, tolerability, PD, and preliminary efficacy data, if available. We also realize that if ≥ 2 patients experience DLT in each of the first two cohorts at founding TAK-659 dose used in the 3+3 escalation, then one (half) dose reduction step of TAK-659 will be needed.

5.2.1 TAK-659 Dose Accommodation with required concomitant dosing anti-fungal agent as moderate activity CYP3A inhibitor

Despite the institution of a more favorable intermittent schedule of the combination of TAK-659 with Ixazomib presented here, when compared to continuous single agent TKI, AML is an intrinsic cause of primary neutropenia leading to fungal infections. Patients considered to have high risk for the development of fungal infection, or with a prior history of an aspergillus/mold infection, now recovered, may require concomitant administration of a moderate CYP3A inhibitor such as fluconazole, or, in the case of the latter ongoing infection more likely to involve aspergillus/mold, isovuconazole. Similarly, patients whom are being treated with benefit, on the existing dose level of the combination, may develop a fungal infection and require isovuconazole.

Patients requiring prophylaxis with fluconazole or patients whom develop active fungal infection, where isovuconazole would be appropriate, continuation of TAK-659 in the combination will require dose reduction to 60mg po daily of the TKI, and careful analysis of toxicity parameters, especially including QTc and hepatic and pancreatic enzymes. Dosing of Ixazomib will not require modification in the absence of relatable toxicity. The above determined TAK-659 dose cannot be escalated. If toxicity supervenes, the patient will be taken off study for alternative anti-infective therapy as needed. Should no toxicity be observed in a cohort, stepwise dose escalation, first to 80mg, may be considered based on review of concurrent PK measurements of specific antifungal impact on TAK-659 levels.

[figure not shown]

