5.3.1 Number of treatment cycles

Given our experience with this sort of treatment algorithm, we will follow the cues previously established in the Sorafenib/Vorinostat/Bortezomib trial to determine the course.

We will follow the peripheral blood blast reduction during the first cycle of therapy. When peripheral blasts have been reduced by at least 50%, we will perform a bone marrow, either day 4 or 8, to document if similar effects are occurring in the marrow as in the periphery. Also, excess cells obtained from the marrow at this early time point will be used to inform the impact of changes in gene signature from baseline marrow, which will have been obtained on the registration/pretreatment visit at day -4 to 0.

Usual supportive care transfusions will occur during the treatment cycle to maintain platelet count >10k at weekly assessments, and hematopoietic growth factors are not mandated as long as ANC >200/uL. Treatment outcome assessment will involve a bone marrow performed at day 15.

Assuming achievement of 50% or greater reduction in marrow blast score (cellularity x blast percentage) after 2 cycles, another cycle will be given. If the patient has had a response (CR, CRp or CRi) after 2 cycles, every attempt will be made to transition the patient to transplant.

However, if the patient is not a transplant candidate but the response after 2 cycles reaches the threshold 50% reduction, continuation of therapy cycles can continue with follow up bone marrow after the next 2 cycles as long as no evidence of peripheral progression occurs. Evidence for progression in the bone marrow would be a cue for discontinuation of therapy.

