Detailed dose modification guidelines are provided in Section 6.2. In the case of TAK-659, which is administered once daily orally, a 1-step reduction of dose (by 20mg) may occur and if toxicity occurs at that dose, a second reduction may be considered. This second reduction will be subject to the judgment of the treating physician. In the case of Ixazomib, further reductions below the -2 dose step reduction from the starting dose that already exists below the RP2D in myeloma is not anticipated.

When a dose reduction occurs, no dose-reescalation will be permitted intrapatient. If study drug dosing is delayed for > 21 days despite supportive treatment per standard clinical practice or more than 2 dose reductions are required in a patient, this patient will have study treatment discontinued.

There exist both unique and overlapping toxicities of TAK-659 and Ixazomib, which will influence dose modification of one or both within the combination. As compared with its predecessor Bortezomib, Ixazomib possesses lower incidence of neuropathy, but the incidence of diarrhea may be higher. However, that diarrhea is usually below grade 3, except in 15-20 % cases in the phase I weekly administration trial. Both Ixazomib and Bortezomib affect thrombocytopenia, but in the context of AML induction therapy, thrombocytopenia is an intrinsic feature, which is supported by transfusion.

By contrast, diarrhea occurs as AE with TAK-659, at 32% rate, and the grade is not high, but in preclinical animal models, gastrointestinal hemorrhage and/or bowel intimal damage was noted at high doses. In the phase Ib C34002 AML trial, the major DLTs included hemorrhage, possibly related to thrombocytopenia, or to functional inactivation of the platelets, at the highest dose of TAK-659: 80 mg po bid. In addition, asymptomatic elevation of lipase, AST and ALT have been observed frequently, but pancreatitis or hepatitis are rare. Pneumonitis felt related to TAK-659 is rare.

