6.3.1 Prophylaxis Against Infection

Patients with advanced hematological malignancies may be at an increased risk of infection. Prophylactic use of antibiotic, antiviral, or antifungal medication can be considered as clinically indicated and as per local standard practice. Ciprofloxacin is considered a standard for patients with ANC <500. Antifungal prophylaxis with fluconazole or isovuconazole which are a moderate CYP inhibitory agents is permitted with dose reduction of TAK-659 as in 5.3.1. Patients requiring prophylaxis with fluconazole or patients whom develop active fungal infection, continuation of TAK-659 in the combination will require dose reduction to 60mg po daily of the TAK-659 with the mold-active agent isovuconazole, and careful analysis of toxicity parameters, especially including QTc and hepatic and pancreatic enzymes. Dosing of Ixazomib will not require modification in the absence of relatable toxicity. The above determined TAK-659 dose cannot be escalated. If toxicity supervenes, the patient will be taken off study for alternative anti-infective therapy as needed. Should no toxicity be observed in a cohort, stepwise dose escalation, first to 80mg, may be considered.

Antiviral therapy such as acyclovir may be initiated as clinically indicated.

The severe and prolonged period of neutropenia seen with therapy is frequently associated with neutropenic fevers and a high risk of infection with bacteria or fungi and viral reactivation. To minimize

the risk of infection, it is recommended that patients be placed on “neutropenic precaution”, with or without the addition of prophylactic antibiotics, antifungals, or antivirals. In addition, patients should be screened for possible infectious foci (eg, dental status).

The components of “neutropenic precaution” while inpatient may vary by institution but most commonly include: a high efficiency particulate air-filtered room, a diet free of raw berries or vegetables grown in dirt, no sick visitors, and no smoking. In addition, hand washing by all visitors and caregivers should be strictly enforced.

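### Sections 5.2.1 and 6.3.1 each both forbid and permit escalation of the antifungal-reduced TAK-659 dose, and only 5.2.1 makes PK review a condition

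*Combined protocol and SAP*

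**What the plan says.** Section 5.2.1 covers patients who need a moderate CYP3A-inhibitor antifungal. For them, "continuation of TAK-659 in the combination will require dose reduction to 60mg po daily of the TKI". It continues: "The above determined TAK-659 dose cannot be escalated". The next sentence takes the patient off study if toxicity occurs. The one after that reads: "Should no toxicity be observed in a cohort, stepwise dose escalation, first to 80mg, may be considered based on review of concurrent PK measurements".

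Section 6.3.1 gives the same reduction to 60 mg and the same prohibition. Its permission is shorter: "Should no toxicity be observed in a cohort, stepwise dose escalation, first to 80mg, may be considered". It ends there, with no mention of PK. For the antifungal rule it refers the reader elsewhere: prophylaxis "is permitted with dose reduction of TAK-659 as in 5.3.1". In the current text that number belongs to "5.3.1 Number of treatment cycles", which does not deal with antifungals.

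Other sections bear on the point:

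- Section 5.2 confines dose escalation to ixazomib. All three planned cohorts carry TAK-659 100 mg.
- Section 13.3 forms the phase II cohorts by Flt3 status.
- Section 6.1 states in one place that a TAK-659 reduction made for toxicity may not be reversed, and in another, without naming a cause: "When a dose reduction occurs, no dose-reescalation will be permitted intrapatient".
- Exclusion criterion 15(b) in section 3.2 gives the reduction to 60 mg and is silent on any later increase.
- Section 14.3 requires sponsor-investigator and headquarters review, and DSMC confirmation, of dose escalation decisions.

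**The concern.** A dosing instruction should let two readers reach the same action. Here the prohibition and the permission stand two sentences apart, in two sections, with nothing to say which governs whom. The two sections also differ on whether plasma levels must be looked at before the step.

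The patients concerned are those whose TAK-659 exposure is least predictable. Section 1.4.3.1 attributes 69.1% to 73.0% of in vitro CYP metabolism to CYP3A4/5 and says that no drug interaction study had been done in humans. A PK check before a dose increase is the one safeguard specific to this situation, and it appears in only one of the two places. Section 5.2.1 sits under the Phase Ib escalation heading, whereas 6.3.1 sits in the general chapter on managing clinical events. A reader looking up infection prophylaxis, particularly in phase II, may well meet only the version without it.

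For the analysis, the TAK-659 dose behind toxicity and response in these patients would depend on how the sections are read.

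**Working it through.** There is no design figure to reproduce. The check is a side-by-side reading, followed by one ratio.

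**1. The two sections compared**

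| Element | Section 5.2.1 | Section 6.3.1 |
|---|---|---|
| Reduction to 60 mg daily | yes | yes |
| Prohibition on escalating that dose | yes | yes |
| Permission for a step, first to 80 mg | yes | yes |
| Trigger: no toxicity in a cohort | yes | yes |
| PK review attached to the step | yes | no |
| Statement that one rule is per patient and the other per group | no | no |

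**2. Does the cross-reference bring the PK condition into 6.3.1?** Not as written. It points to 5.3.1, which concerns the number of treatment cycles. The table of contents lists Phase Ib Dose Escalation as 5.3, so the pointer is probably old numbering for what is now 5.2.1. Even then, the pointer is attached to the dose reduction, not to the later step.

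**3. Which cohort is meant?**

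- *A phase I dose cohort (5.2).* These are ixazomib levels at TAK-659 100 mg. The 80 mg rows in the 5.2 tables are reductions from 100 mg after DLT, not increases from 60 mg. A cohort free of toxicity at 100 mg without an antifungal says little about 60 mg with one.
- *A phase II cohort (13.3).* These are defined by Flt3 status, not by antifungal use.
- *A group of antifungal-treated patients at 60 mg.* This fits the sense of the sentence best, but no such group is defined. No size, observation window or toxicity count is given for it.

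**4. Do the rules in 6.1 settle it?** No. If the unqualified intrapatient rule covers every reduction, it supports reading the prohibition as per patient. If, like the earlier sentence in 6.1, it concerns only reductions made for toxicity, it does not reach a reduction made because of an antifungal. The documents do not say which.

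**5. Size of the permitted step.** Inputs: 60 mg and 80 mg, both from 5.2.1.

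(80 − 60) / 60 = 20 / 60 = 0.33, an increase of 33%.

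The antifungal's effect on TAK-659 exposure is not given, so the exposure that results from the step cannot be computed from the documents.

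**The case against.** The best defence is that the text makes sense if read with care. The sentence after the prohibition speaks of the patient, the permission speaks of a cohort, and 6.1 has an intrapatient bar. Together these suggest that a reduced patient stays at the reduced dose while a later group may start higher. The 5.2 cohorts also come with 3 to 6 patients, a two-cycle window and DLT counts that could supply the missing terms, and 6.3.1 may simply abbreviate 5.2.1.

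Much of this stands as a plausible account of intent. It does not remove the defect: neither section states the distinction, the borrowed cohort rules were written for a different set of patients, and the abbreviation drops the one condition specific to the step.

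The objection does defeat several stronger readings that a reader might draw:

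- *That the same patient may plainly be either kept or escalated, as a site prefers.* The patient-level reading of the prohibition is at least as natural, the permission says only that a step may be considered, and section 14.3 puts escalation decisions before the sponsor-investigator and the DSMC. The limit is that 14.3 does not mention antifungal-treated patients and does not clearly reach a change within one patient.
- *That section 6.1 is a further clear contradiction.* It may support the patient-level reading or may not apply.
- *That 80 mg with an antifungal would approach or exceed the single-agent limits.* Section 1.4.6 gives 140 mg as RP2D and 160 mg as MTD for once-daily TAK-659, but for continuous single-agent dosing, whereas this trial gives 15 of 21 days in combination. The fold-increase needed for the comparison is in neither the protocol nor the SAP text.
- *That the dose would be uncontrolled.* Administration is recorded (5.6) and plasma levels are sampled in all patients (8.4).

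**Conclusion.** The point holds as an internal inconsistency. Two operative sections each contain a prohibition and a permission on the same dose without saying to whom each applies, and they differ on whether PK review is a condition. No group of antifungal-treated patients exists in the design to which the permission could attach.

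The size that the documents support is a 33% dose step in patients with an unquantified interaction. How many patients would be affected is not stated and is not estimated here; section 5.2.1 itself treats the need for an antifungal as foreseeable in this disease. The conclusion rests only on the wording of the sections and on no assumed inhibitor effect. It does not show that any stated dose limit would be exceeded, and it takes no view on which dosing rule is correct.

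**What to change.** Reconcile 5.2.1 and 6.3.1 with each other and with the restriction of escalation to ixazomib in 5.2. The amended text should:

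1. State whether the prohibition applies to the individual patient, and whether the permission applies to that patient or to a defined group. If a group, define it, including how many patients must complete which observation window and what toxicity finding allows the step.
2. State whether PK review is a condition of the step, in the same terms in both sections.
3. Say whether the no-re-escalation rules in 6.1 cover reductions made because of an antifungal.
4. State that the step goes through the review in section 14.3.
5. Correct the reference to 5.3.1 in section 6.3.1.

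Which rule to adopt is for the sponsor and investigators.

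The cost is protocol wording. PK samples are already scheduled through Cycle 4 Day 15 (8.4). If PK review is kept as a condition, the text should also say what it relies on when an antifungal is started after that point.

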5.2.2 Dose Reduction or Discontinuation in the setting of Pneumonitis

Should the patient develop grade 1 or 2 pneumonitis, the combination therapy will be held until the episode resolves and the TAK-659 and Ixazomib doses will undergo 1-step reductions, respectively. If the episode recurs the patient will be taken off study. Similarly, should the patient develop grade 3+ pneumonitis, permanent drug discontinuation will be required.

5.3 Dose Escalation Rules and MTD Definition

Dose escalation will be determined based on the number of toxicities as noted by the algorithm noted in the following Figure 5-1.

Figure 5-1 Dose/Schedule Escalation Algorithm TAK-659 and

TAK-659/Ixazomib Clinical Study Protocol

If 2 or more patients in any dose level experience DLT, enrollment at that dose level will stop. Following consultation between the sponsor and investigators, either the previous dose level will be considered the MTD (if 6 or more patients have been studied at that dose level), the previous dose level will be expanded (if fewer than 6 patients have been studied at that dose level), or a dose level intermediate between the current and the previous dose level will be evaluated.

To define the Maximum Tolerated Dose (MTD), subjects will be evaluated for DLT following two cycles (56 days) of treatment. Decisions to move to next dose escalation cohort will not be made until all subjects complete 2 cycles of therapy at a given dose.

The MTD is defined as the dose level at which fewer than 33% of subjects experience a dose limiting toxicity (DLT), and specifically is the dose level at which less than 2 out of 6 subjects experience DLT. The minimal safe and effective dosing with pharmacodynamic and pharmacokinetic parameters pointing toward the goal of efficacy optimization, will be the recommended dose (RP2D) for the Phase II component of the study. To achieve this, the developing results of safety, tolerability, efficacy, PK and PD in each dose-escalation cohort will be reviewed in real time after each cohort, to determine whether maximal safety and evolving efficacy milestones will have been reached based on examination of two consecutive cohorts, when safety and tolerability measures are within criteria for each.

- The criterion for safety will be DLT <20% within the cohort.
- The criterion for tolerability will be the administration of >80% of expected dose within the cohort.
- The criterion for efficacy will be the dose with an estimation of greater or equal to 25% ORR in the Flt3 mutant cohort, or greater than or equal to 10% ORR in the Flt3 wild-type cohort.
- The criterion for optimizing PK will be: on day 1, equal or greater than 100ng/ml peak (Cmax) TAK-659, or its trough equal or greater than 15ng/ml; on day 15, peak at least 200ng/ml, trough at least 40ng/ml. On the other hand, the day 15 peak should be less than 400ng/ml, and trough should be less than or equal to 100ng/ml.

- The criteria for defining an optimization of PD will be the reduction in more than one of the epigenetic drivers by 50%: JUN, ID1, β -catenin, HOXA 9/10, MEIS1 or rise by 50% of the epigenetic repressor RUNX3.

Subjects will initially be enrolled onto dose level 1. Three to six evaluable subjects will be enrolled at each dose level. All subjects assigned to a dose level must be followed for at least 2 cycles before dose escalation to the next cohort level can begin.

Note: Subjects not evaluable for DLT assessment (i.e. do not complete at least 1 cycle of therapy due to reasons other than toxicity) on the Phase I portion of the protocol will be replaced for determination of dose escalation.

The following rules will be followed:

- An initial three subjects will be enrolled in cohort 1. If all 3 subjects in cohort 1 complete 2 cycles of therapy without dose limiting toxicity (DLT), the study will proceed to enroll 3 subjects at cohort 2. If all 3 subjects in cohort 2 complete 2 cycles of therapy without DLT, the study will proceed to Phase II with the MTD of each drug established.
- Alternatively, if 1 of the first 3 subjects in any given dose cohort experiences DLT, an additional 3 subjects will be enrolled at that dose level. If only 1 of the total 6 subjects in a dose level experience DLT, the study will proceed to the next dose level as planned. If 2 of the total 6 subjects in any given dose cohort experience DLT, the next lower dose level will be explored and considered the maximum tolerated dose (MTD) if no more than 1 of 6 subjects experience a DLT. That dose will be recommended for the Phase II study.

Number of subjects with DLT at given dose level	Escalation decision
0 out of 3	Enter 3 subjects at the next dose level.
≥ 2 out of 3	Dose escalation will be stopped. This dose level will be declared the maximum administered dose . Three (3) additional subjects will be entered at the next lower dose level if only 3 subjects were treated previously at that next lower dose level.
1 out of 3	Enter at least 3 more subjects at this dose level: 
 • If 0 of these additional 3 subjects experience DLT, proceed to the next dose level. • If 1 or more of these additional 3 subjects experience DLT, then dose escalation is stopped and this dose is declared the maximum administered dose. Three (3) additional subjects will be entered at the next lower dose level if only 3 subjects were treated previously at that dose.
≤ 1 out of 6 at highest dose level below the maximum administered dose	This will be defined as the MTD. This dose level will be the recommended Phase II dose.

